5. LIST OF ABBREVIATIONS

ACASI	Audio Computer Assisted Self-interviews
AE	Adverse Event/Adverse Experience
AIDS	Acquired Immunodeficiency Syndrome
ART	Antiretroviral Therapy
ARV	Antiretroviral
CAB	Community Advisory Board
CAPI	Computer Assisted Personal Interview
CCC	Comprehensive Care Center
CCT	Conditional Cash Transfer
CDC	U.S. Centers for Disease Control and Prevention
CRF	Case Report Form
DAIDS	Division of AIDS
DBS	Dried blood spots
ERC	Ethics and Research Committee
GCP	Good Clinical Practice
HAPI	HIV and Pregnancy Intention
HIV	Human Immunodeficiency Virus
HTS	HIV Testing Services
HPTN	HIV Prevention Trials Network
IC	Informed Consent
ICER	Incremental Cost Effectiveness Ratio
ICF	Informed Consent Form
ICH	International Conference on Harmonization
IEC	Independent or Institutional Ethics Committee
IRB	Institutional Review Board
IRDO	Impact Research and Development Organization
KNH	Kenyatta National Hospital
MOH	Ministry of Health
MP3	Methods for Prevention Packages Program
N	Number (typically refers to participants)
NASCOP	National AIDS and STI Control Programme
NGO	Non-Governmental Organization
NIAID	National Institute of Allergy and Infectious Diseases, NIH
NIH	National Institutes of Health
OF HIVST	Oral Fluid HIV Self-testing
OHRP	Office for Human Research Protections
PEPFAR	President's Emergency Plan for AIDS Relief
PI	Principal Investigator
PITC	Provider-initiated Testing and Counseling
PIMA Analyzer	Pima CD4 test delivers an absolute count of T-helper cells from either a finger stick or venous whole blood sample within 20 minutes

PMTCT	Prevention of mother-to-child transmission
POC	Point of Care
PrEP	Pre-Exposure Prophylaxis
PSRC	Prevention Science Review Committee
PSRT	Protocol Safety Review Team
PTID	Participant Identification Number
RA	Research Assistant
RE	Regulatory Entity
QA	Quality Assurance
QC	Quality Control
SAE	Serious Adverse Event/Serious Adverse Experience
SES	Socioeconomic status
SMC	Safety Monitoring Committee
SMS	Short Message Service
SOP	Standard Operating Procedure
SSA	sub-Saharan Africa
SSP	Study-Specific Procedures (manual)
STIs	Sexually Transmitted Infections
UCT	Unconditional Cash Transfer
UN	United Nations
UNAIDS	The Joint United Nations Programme on HIV/AIDS
UNICEF	The United Nations International Children's Emergency Fund
UoN	University of Nairobi
USSD	Unstructured Supplementary Service Data
VCT	Voluntary counseling and testing
VL	Viral Load
VMMC	Voluntary Medical Male Circumcision
WHO	World Health Organization

6. PROTOCOL SUMMARY

Full Title	High-yield HIV testing, facilitated linkage to care, and prevention for female youth in Kenya
Short Title	GIRLS Study
Principal Investigator(s)	[name], CNM, MPH, FAAN [name], MPH [name], MPH
Sample Size	(N=1200). HIV positive cohort: (N≈108) ^a ; Subset of HIV negatives (N≈185)
	^a note that the positive cohort is an estimate based on expected HIV prevalence
Study Population	Female youth (aged 15-24) from Homa Bay County, Nyanza region, western Kenya
Study Design	The GIRLS study will rigorously compare two ‘seek’ recruitment strategies, three ‘test’ strategies, and two enhancements to an adaptive (SMART trial design) ‘linkage’ to care intervention, among young at-risk women, 15-24 years old, in Homa Bay County, western Kenya. Additionally, we will evaluate a scalable primary prevention messaging intervention to support identified HIV-negative young women in reducing HIV risk and adhering to HIV re-testing recommendations. This study design will allow us to follow participants along both the prevention and care continua.
Study Sites	The study will take place in Homa Bay County, Nyanza region, Kenya. 
 • Homa Bay municipality • Mbita sub-county • Ndhiwa sub-county
Study Duration	Anticipated 12 months of accrual with 12 months of follow-up.
Study Intervention Description	
The following will be offered to all female youth (N=1200):
 
 (1) HIV Testing Services (HTS) via home-based or community based recruitment strategies (2) HIV testing approaches that females can choose from include: (a) oral fluid HIV self-testing (OraQuick ADVANCE® Rapid HIV-1/2 Antibody Test, OraSure Technologies) at their convenience; (b) staff-aided testing at home/mobile site; and (c) a referral to a health care facility where HIV testing will be done by a health care provider (standard facility-based HTS) (3) Behavioral survey at baseline visit (4) SMS HIV test experience satisfaction survey (5) Staff-administered questionnaire about self-testing for females who choose self-testing option. 
For all HIV positive females:
 
All HIV positive females will receive the following;
 
 (1) Point of care (POC) CD4 cell count at baseline (2) Viral load testing using dried blood spot (DBS) at 0 and 12 months (3) Referral for care and treatment; Adaptive linkage to care intervention. All HIV positive participants (N≈108) will be randomized to receive standard referral (N≈54) or standard referral plus SMS message (N≈54) to link to HIV care and treatment services; those who do not link to care within 2 weeks will be re-randomized in a ratio of 1:1 to a second SMS message or a one-time economic incentive to link to care.

	
We will confirm linkage by self-report via phone call, and verified by medical record review.
 
(4) ART adherence and treatment SMS reminders, combined with health status surveys at 3, 6, 9, and 12 months aligned to school holidays for those in school, when the participants would have access to phones.
 
(5) Face-to-face (or telephone) interview on barriers and facilitators to seeking HIV care services after receiving a positive diagnosis at 12 months. If a phone interview is conducted, participant's identity will be confirmed by asking the participant to provide three names used at enrollment as well as their current age, so that her identity may be ascertained correctly.
 
For HIV negative females:
 
All HIV negative females will receive the following:
 
Risk assessment counseling, condoms, and referral for other prevention services (partner and family testing, PrEP, other family planning (contraception) methods, STI screening and treatment, drug use counseling, mental health services, social and nutritional support, legal services, sexual and gender based violence services and others that might be identified during the interview/risk assessment with participants).
 
A subset of randomly selected high risk (risk score ≥ 2 as defined by eligibility criteria for high risk) HIV negative females ($N \approx 185$) will receive:
 
 (1) An SMS text at 6 and 12 months with a health promotion message; (2) SMS survey to collect HIV risk behaviors, condom use, and willingness to retest for HIV at 6 and 12 months; (3) HIV test at 12 months; (4) Face-to-face (or telephone) interview on barriers and facilitators to accessing HIV prevention services at 12 months. If a phone interview is conducted, participant's identity will be confirmed by asking the participant to provide three names used at enrollment as well as their current age, so that her identity may be ascertained correctly.
Primary Objectives	
(1) To determine the preferred recruitment venue and testing modality that targets and finds the highest number of HIV infected and at risk female youth aged 15-24 years in Homa Bay County, Nyanza region, western Kenya (Aim 1).
 
 • This will be determined by examining the uptake and yield of previously undiagnosed HIV infection of the two (2) 'seek' strategies (community or home-based) and the three (3) 'test' strategies (self-testing, HTS in a home/mobile setting, or facility-based HTS) among female youth; 
(2) To conduct an economic evaluation, using cost effectiveness analyses to determine the relative utility of each seek, test, link, and prevention intervention (Aim 3).

Secondary Objective	
(1) To pilot and evaluate an adaptive intervention to link newly diagnosed HIV-positive female youth to treatment and care services (Aim 2a);
 
(2) To identify barriers and facilitators to seeking HIV care services after receiving a positive diagnosis (Aim 2b);
 
(3) To identify barriers and facilitators to seeking HIV prevention services for high risk female youth after receiving a negative HIV test result (Aim 2c);

	(4) To provide an HIV prevention intervention to a randomly selected subset of high risk negatives (N≈185) (motivational text message, with referral for combination prevention interventions), and to re-test them at 12 months (Aim 2d).
Primary Endpoint(s)	
Primary outcomes of interest for Aim 1 are based on the HIV prevention and treatment continua as outlined below:
 
 • Recruitment/Seek: Ability to identify and recruit female youth that are high risk for HIV infection using two seek strategies (home-based vs. community-based) 
 ○ The proportion of youth in the community who accept study screening (estimated from total youth approached as the denominator); ○ The proportion of youth who accept study enrollment (estimated from youth screened and eligible as the denominator); • Testing: 
 ○ Testing uptake by different testing modalities; ○ Completion of confirmatory testing; ○ Proportion that are positive; ○ Among those who are positive, completion of baseline collection of CD4 and viral load tests. 
Outcomes of interest for Aim 3 economic evaluation to determine the comparative cost effectiveness of the seek, test, link, and prevention interventions are:
 
 • Compute the cost per HIV-infected female youth identified under each 'seek' strategy (home-based vs. community based); • Compute the cost per HIV-infected female youth identified under each 'test' strategy (self-testing, staff delivered HTS testing, standard facility-based HTS); • Calculate the incremental cost-effectiveness ratio of the adaptive linkage to care intervention among HIV positive female youth; • Compute the cost of the SMS prevention intervention among HIV negative female youth.
Secondary Endpoint(s)	
Secondary outcomes of interest for Aim 2 are based on the HIV prevention and treatment continua as outlined below:
 
 • Linkage to Care: 
 ○ Percent of females who tested positive that attended a first HIV care appointment at an HIV Comprehensive Care Center (CCC) ○ Time to link to care after positive confirmatory test result. • Retention in Care: 
 ○ Completion of viral load testing at 12 months; ○ Reported appointment attendance via SMS and verification by study staff at 3, 6, 9, and 12 months. • Primary Prevention (N≈185): 
 ○ Proportion reporting HIV risk behaviors, and condom use, at 6 and 12 months; ○ Proportion who re-tested at 12 months; ○ Proportion who tested positive at 12 months.

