conducted, participant's identity will be confirmed by asking the participant to provide three names used at enrollment as well as their current age, so that her identity may be ascertained correctly. **Those not enrolled into the cohort will be referred for prevention and other services** (partner and family testing, PrEP, other family planning (contraception) methods, STI screening and treatment, drug use counseling, mental health services, social and nutritional support, legal services, sexual and gender based violence services and others that might be identified during the interview/risk assessment with participants).

Follow Up SMS Surveys

Participants will be educated on how to complete surveys on their phone at the time of enrollment. At this time, their cell phone number will be linked to their study ID. Each participant will be assigned a unique password/PIN code and a memory word. When they are sent the survey, they will need to enter their password to participate. If the participant forgets their password, they will be required to enter their memory word and if this fails, they will be required to visit the study site in person for identity verification and allocation of a new pass word. Once study staff ensures that the phone user is the study subject, (receiving texts is free in Kenya) staff will then wirelessly transfer airtime, so the cohort participant can send surveys using short message service (SMS) texting (Kumar, Chen, Paik, & Subramanian, 2009). In this way we will ensure follow up with the cohort regardless of where they live (if they moved since baseline). The SMS surveys will collect the following types of information, including but not limited to:

- HIV testing option and test experience
- Successful linkage
- Sexual risk behaviors
- Retention in care
- Adherence barriers and facilitators
- Willingness to re-test (for subset of HIV negatives)
- Status disclosure

[figure not shown]

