17.4 Participant Confidentiality

All study staff will be trained on participant confidentiality. All study staff will hold all aspects of the study (protocol documentation, and all other study related documents) in the strictest confidence. No information concerning the study or data will be released to any unauthorized third party, without written permission from the sponsor and the study participant.

The study monitors (Yale, KNH, IRDO), other local, US, and international regulatory entities, and IRBs/ECs, or other authorized representatives of the sponsor (e.g., monitors, DAIDS, and OHRP) may inspect all documents and records required to be maintained by the Investigator, including but not limited to, medical records (office, clinic or hospital) for the participants in this study.

See section 18: Data Handling and Record Keeping for additional information on participant confidentiality.

We will ensure confidentiality with mobile phone usage confirming user identity for SMS messages as well as airtime incentive and digital cash transfers. (See data management responsibilities section).

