18.2 Data Capture Methods

18.2.1 Data Collection

All participants who are eligible, consented, and registered for the GIRLS study will be required to complete a baseline behavioral CAPI survey and an HIV testing experience satisfaction SMS survey. HIV positive participants who have successfully linked to care will complete SMS surveys every 3 months as described in the study procedures section. A subset of the HIV negative participants will also complete SMS surveys at 6 and 12 months. The HIV positive cohort and the HIV negative cohort will also complete a face-to-face (or telephone) interview at 12 months. If a phone interview is conducted, participant's identity will be confirmed by asking the participant to provide three names used at enrollment as well as their current age, so that her identity may be ascertained correctly.

Administering Computer Assisted Personal Interview (CAPI) Surveys – interviewer assisted.

- **Data Collection Setup**
 1. The CAPI will be staff-administered on a tablet computer.
 2. All survey questions will be pre-programmed in tablet by the IT Officer and the Data Manager who will be responsible for training the field staffers and other study personnel on their use.
 3. The CAPI will be administered by the RAs/Counselors.
 4. Once a participant is enrolled in the study, her screening data will be entered into the main database in the study IT Office.
- **Data Collection Procedures**
 1. Participants are required to complete the baseline survey.
 2. The behavioral CAPI survey will be administered after IC. The survey should be completed in one sitting.

3. For sensitive questions, the participant can input the answer without the interviewer viewing the screen, to reduce discomfort.
4. Once complete, the RA will thank the participant for completing the survey.

- **Data Transfer Process**

1. All data will be temporarily saved on the hard-drive of the tablet.
2. The data from the tablets will then be securely uploaded to the IT Office Data Computer and then securely transferred to the Data Manager's office in Nairobi where the GIRLS study database will be housed. This transfer will occur within 12 hours after completion of data collection.
3. Data will not be deleted from the tablets before it is uploaded onto the IT Officer's Data Computer and has been transmitted to Nairobi Office.

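### The 12-month telephone exit interview checks identity only by names and age, although the study already issues each participant a PIN and a memory word

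*Combined protocol and SAP*

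**What the plan says.** Section 6 (Study Intervention Description) allows the 12-month interview to be face-to-face or by telephone in both cohorts. On the telephone route, the "participant's identity will be confirmed by asking the participant to provide three names used at enrollment as well as their current age". The same rule appears in section 7.4 (rationale for the cash transfer), section 11.6.2 (HIV-negative cohort), section 11.8 and section 18.2.1. The last of these covers both groups: "The HIV positive cohort and the HIV negative cohort will also complete a face-to-face (or telephone) interview at 12 months".

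For HIV-positive participants the subject of the interview is "barriers and facilitators to seeking HIV care services after receiving a positive diagnosis at 12 months". For HIV-negative participants it is access to prevention services, and section 11.6.2 admits to that cohort only those classed as high risk.

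Follow-up SMS surveys are handled differently. Under that heading in section 11.6.2: "Each participant will be assigned a unique password/PIN code and a memory word". The password is a condition of taking part: "When they are sent the survey, they will need to enter their password to participate". A participant who forgets it enters the memory word. If that fails, "they will be required to visit the study site in person for identity verification and allocation of a new pass word".

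Section 17.4 gives a general assurance: "We will ensure confidentiality with mobile phone usage confirming user identity for SMS messages as well as airtime incentive and digital cash transfers". Spoken interviews are not in that list.

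There is also an earlier call, about linkage. Section 6 says: "We will confirm linkage by self-report via phone call, and verified by medical record review". The protocol states no identity check for it.

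**The concern.** The protocol asks for a code before a participant may answer a text survey, but accepts biographical facts before a live conversation about HIV care. The people most likely to be near the phone, such as a parent, sibling or partner, can be expected to know her names and age. Someone who passes the check is then asked questions that presuppose a positive diagnosis or, in the other cohort, high-risk status.

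The protocol itself shows why this matters. Sections 15.9 and 17.5.1 list stigma, discrimination, loss of social support and physical or verbal abuse as possible harms. Section 17.2.1 lets a non-emancipated minor who chooses staff-aided testing keep her result from the parent who consented, provided that she names a guardian to whom she will disclose a positive result. The parent she has excluded is someone who would pass a names-and-age check.

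A lesser stake is data quality: answers from the wrong person could enter the barrier and facilitator interviews of Aims 2b and 2c.

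**Working it through.** The plan gives no figure to reproduce. The check is a comparison of procedures, followed by the size of the exposed group.

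**1. Identity checks by type of contact**

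| Contact | Check stated in the protocol | If the check fails | Where |
|---|---|---|---|
| Follow-up SMS survey | Password/PIN, then memory word | In-person verification | 11.6.2, Follow Up SMS Surveys |
| 12-month telephone interview | Three enrolment names and current age | None stated | 6, 7.4, 11.6.2, 11.8, 18.2.1 |
| Linkage call | None stated | None stated, but the answer is verified in medical records | 6 |

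**2. Is the code available when the calls are made?** Section 11.6.2 sets up the SMS survey arrangements at enrolment. Appendix A schedules an SMS survey at 12 months in both cohorts, the same time as the exit interview. The credential should therefore still be in use at the exit interview, and should already exist at the linkage call.

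**3. Who is exposed?** The upper limits are the cohort sizes in section 6.

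- HIV status revealed by the topic: at most about 108.
- Participation and high-risk classification revealed: at most about 185.
- Interviews whose data could be affected: at most 108 + 185 = 293.

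These are ceilings, because telephone is an alternative to a face-to-face interview.

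**4. Can the number of wrong-person calls be estimated?** Not from the documents, which give neither the telephone share nor an impersonation rate. For scale only, assume that 20% to 50% of interviews are by telephone and that 1% to 3% of those are answered by someone posing as the participant. Neither range has any support in the documents.

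- HIV-positive cohort: 108 × 0.20 = 21.6 to 108 × 0.50 = 54 calls. Wrong-person calls: 21.6 × 0.01 = 0.2 to 54 × 0.03 = 1.6.
- Both cohorts: 293 × 0.20 = 58.6 to 293 × 0.50 = 146.5 calls. Wrong-person calls: 58.6 × 0.01 = 0.6 to 146.5 × 0.03 = 4.4, which is 0.2% to 1.5% of 293.

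Even on these invented rates, the effect on descriptive interview data is small.

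**5. Does the linkage outcome depend on the call?** Section 11.6.1 defines linkage as a first clinic appointment with registration and a patient number, and commits the study to verifying whether and when the participant reached the clinic. Section 11.8 adds a tracking card and a check with the clinics. Table 1 lists medical record review at the care centre as a source. A false answer on the telephone would have to survive that check.

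**The case against.** The strongest reply is that the failure needs deliberate impersonation. Someone who merely picks up must pose as the participant and supply three enrolment names and her age. That relatives know these facts is an inference, not something the documents state. Cohort members are given a low-cost phone (sections 11.6 and 11.6.2), which reduces the chance that another person answers. Section 11.6.3 places the HIV-positive exit interview at the study sites, at the visit where the viral load specimen is taken, so few calls may be made. All of this lowers the frequency. It does not remove the gap: household members are the people best placed to pass the check, and section 6 itself times the HIV-positive surveys to school holidays because participants in school may lack phone access at other times.

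Two further objections concern the remedy. A code spoken aloud may be overheard, and an in-person fallback may lose participants who have moved, whom the telephone serves best. Both stand as costs. Using the memory word instead of the PIN limits the first, though not entirely, since the word is also the backup for SMS surveys.

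The study-specific procedures manual is not among the documents and the consent forms were removed from the review copy. A call-script safeguard there cannot be excluded; the protocol text contains none.

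A reader might infer that a wrong person's answer on the linkage call could corrupt the status used for re-randomisation. The documents do not support this, because linkage is verified against clinic records. The concern about that call is disclosure. A reader might also count all 293 interviews as possible disclosures of a positive status. Only the HIV-positive cohort, at most about 108, carries that risk.

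**Conclusion.** The point holds as a privacy weakness with an inexpensive remedy. The telephone check rests on facts that close contacts can be expected to know, while a better credential is already in participants' hands and is required for less exposed contacts. Its frequency cannot be quantified from the documents. One disclosure to a partner or parent cannot be undone, which justifies the change even if such calls are rare.

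The consequence for inference is slight. The Aim 2b and 2c interviews are the main data exposed; 12-month viral load and HIV re-test results come from specimens.

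The conclusion assumes that relatives or partners know the names and age, that some exit interviews are in fact done by telephone, and that no stronger check sits in documents not available here.

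**What to change.** In sections 6, 7.4, 11.6.2, 11.8 and 18.2.1, add the memory word as a required identity check for every telephone interview, to be passed before the caller mentions HIV, the clinic or the study topic. Prefer the memory word to the PIN, so that the main SMS credential is not spoken aloud. Apply the same check to the linkage-confirmation call in section 6. If it fails, use the in-person verification already described in section 11.6.2.

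In the same edit, reconcile section 11.6.3, which describes the HIV-positive exit interview at the study sites only, with the telephone option in sections 6 and 18.2.1, so that it is clear when a call may replace the visit.

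The cost is a change to the protocol wording and the call script, using codes already issued. A few telephone interviews may be delayed or lost, mainly among participants who have moved or forgotten the word.
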